Females who are able to have children will also have a urine pregnancy test at evaluation, and week 6 or study completion. If a participant has a positive pregnancy test she will not be able to take part in the study. As detailed in the exclusion criteria, all participants will be required to use contraception adequate to avoid conception, or to not participate. In the event that a subject becomes pregnant, we will ask the subject's permission to obtain information about the outcome of the pregnancy and the condition of the newborn. In the event that a subject reports contributing sperm to a pregnancy during the study period, we will also ask the subject's permission to obtain information about the outcome of the pregnancy and the condition of the newborn. Those subjects who terminate study participation before the completion of the study will be asked to complete all tasks scheduled to take place on the final study visit at the time of study discontinuation.

We will increase our chances of identifying exclusionary mental health conditions by supplementing the clinical interview for study eligibility with review of self-report on the Adult Self-Report (ASR), a self-report scale validated to identify major mental health conditions, prior to participation.

Subject Dosing and Visit schedule:

Visits will occur for evaluation, baseline, and weekly for weeks 1, 2, 3, 4, 5 and 6. Visits will be conducted at 7 day intervals, +/- 3 days. Doses will be assigned at each study visit for the period of time until the next visit, with forced-dose up-titration as tolerated from 75 mg at week one to 150 mg at week 2, and with intention that dosing remain stable for the last four weeks of study participation, such that investigators will ask a subject to go back down to 75 mg during any of the weeks following week 2 only if only if 150 mg is not tolerated. Thus, the most robust titration would be 75 mg until week 1, and 150 mg for the rest of study. The least robust titration where a subject maintains participation would be 75 mg for the duration of the study.

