This study will preferentially utilize synchronous visit telemedicine assessments in all visits to minimize subject burden. Efforts to maximize subject safety and convenience will include the option to have in-person meetings if public health conditions allow or are preferred by either a subject or study clinicians. Throughout the study, efforts will be made to maximize comfort of subjets primarily and, secondarily, meaningful research participation.

Subjects will be offered treatment follow-up for two visits with staff at the MGH Clinical and Research Program in Pediatric Psychopharmacology at the end of the study to facilitate transition to ongoing care. Subjects who complete the study will have the option of receiving two clinical care visits (one approximately monthly appointment over up to three months' time) at the completion of the study in which they will be seen by study staff. The three months of follow-up care are a courtesy that is offered to help find long-term care if needed. Subjects will receive referrals to clinicians in their communities. No research data will be collected at these follow-up visits.

Phone calls will be conducted by a study research assistant before and during visits to assess medication compliance and change in medication treatments. Pill counts will be done by study staff at every other study visit by visualization in person or by remote televisit. At any time, contact can occur by phone or in person as needed with a clinician or research assistant, based on the judgement of the study staff, or by needs of the subjects as they arise. Study clinicians are also available to subjects 24 hours each day by pager.

Randomization and Maintenance of double-blind

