- Adult ADHD Investigator Symptom Rating Scale (AISRS). Each of the individual symptoms of ADHD is rated 0 to 3 on a scale of severity.
- Adverse Experiences (collected at all visits excluding the screening and baseline visits) and Concomitant Medications.

Subject rated scales (all scales rated at baseline and week 6 or drop visit:

- The 18-item ADHD Rating Scale to evaluate frequency of ADHD symptoms on a scale of 0 to 4 (ADHD-RS).
- The 86-item Behavior Rating Inventory of Executive Function Adult Form (BRIEF-A) to assess levels of executive function deficits.
- Pittsburgh Sleep Quality Index. This Index is a widely used measure which consists of 19 items which assess sleep quality over one month time period.
- Epworth Sleepiness Scale

Subject rated scale at baseline only

 In addition, at baseline the The Adult Self-Report Form (ASR) to measure a wide range of psychiatric syndromes (i.e., depressive problems, anxiety problems, antisocial personality problems) in adults. The ASR provides dimensional scale scores for each syndrome that are age- and gender-normed. ²⁶

Adverse Event Assessment and Reporting

All solriamfetol treatment-emergent serious adverse events (initial and follow-up) that require collection per protocol will be reported to Axsome Therapeutics via email within 1 business day of awareness of the serious adverse event.

As noted above, adverse events will be recorded at all visits other than screening and baseline. Investigators will characterize adverse event by description, note the severity (mild, moderate, or severe), whether it is expected (yes or no), relatedness (unrelated, definite, probable, or possible).

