- (3) the basis for determining that the event is related or possibly related to the research procedures;
- (4) the basis for determining that the research places subjects at an increased risk of harm (i.e., a serious adverse event); and
- (5) whether any changes to the research or other corrective actions are warranted

Such unanticipated problems involving risks to subjects or others will be submitted to the Human Research Committee within 5 working days/7 calendar days of the date the investigator first becomes aware of the problem.

Serious adverse event means any event temporally associated with the subject's participation in research that meets any of the following criteria:

- results in death;
- is life threatening (places the subject at immediate risk of death from the event as it occurred);
- requires inpatient hospitalization or prolongation of existing hospitalization:
- results in a persistent or significant disability/incapacity;
- results in a congenital anomaly/birth defect; or
- any other adverse event that, based upon appropriate medical judgment, may jeopardize the subject's health and may require medical or surgical intervention to prevent one of the outcomes listed above (examples of such events include allergic bronchospasm requiring intensive treatment in the emergency room or at home, blood dyscrasias or convulsions that do not result in inpatient hospitalization, or the development of drug dependency or drug abuse).

Data Collection:

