Examples of individuals who will discontinue study participation include those who: 1) develop intolerable adverse events (AEs) despite dose adjustments; 2) have (a) clinically relevant serious AE(s) as determined by the investigator; 3) have worsening ADHD symptoms (much worse or very much worse as rated on CGI-Improvement at two consecutive visits); or 4) have emergent adverse mental health state including psychosis, suicidality, substance use, or worsening mood and/or anxiety; 5) are non-adherent to study procedures or withdraw from the study; 6) intend to be or become pregnant.

If study participation is discontinued due to safety reasons, participants will receive two followup visits, giving adequate time for appropriate psychiatric referrals to treaters in their communities. Subjects found to be taking substances listed as exclusionary during the course of the study may be discontinued based on PI evaluation of their eligibility.

VI. BIOSTATISTICAL ANALYSIS

Data processing and management followed procedures developed by the investigators and used in ongoing studies. Up to 30 subjects will receive Solriamfetol, and up to 30 subjects will receive placebo. Changes in outcome ratings within and between study groups will be tested.

Hypothesis 1 will be our main testable hypothesis, tested by evaluating whether the group receiving stimulant treatment has a significantly greater improvement in ADHD symptom rating. We will also explore exploratory hypotheses. This will include comparing the active and placebo arms on: the rate of individuals achieving an a priori definition of clinical improvement, with at least a 25% reduction in ADHD symptoms, and a CGI of much or very much improved (1b), and the rate of reduced symptoms of executive dysfunction (defined by a 0.5 standard deviation improvement on BRIEF-A self-report total or subscale scores) (1c).

All other analyses will be exploratory and p-values will be reported as nominal, and not used to infer significance. We will also explore descriptively whether baseline sleep problems, sleepiness, or deficits in domains of the BRIEF predict improvement on AISRS or BRIEF ratings.

Our primary test of Hypothesis 2 will be review of the occurrence of moderate or severe adverse events, and description of reasons for study dropout. We will also report rates of the same adverse event in active and placebo arms occurring two or more times for a particular subject.

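### Adverse-event collection stops at the Week 6/drop visit, with no post-dose window, no rule for open events and no safety exemption from the bar on data at later visits

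*Combined protocol and SAP*

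**What the plan says.** **Study visits.** Section V, Subject Dosing and Visit schedule: "Visits will occur for evaluation, baseline, and weekly for weeks 1, 2, 3, 4, 5 and 6". Doses are assigned at each visit to last until the next.

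**Adverse events.** Section V, Adverse Event Assessment and Reporting: "adverse events will be recorded at all visits other than screening and baseline". Each event is characterised by description, severity, expectedness and relatedness. In the Visual Timeline, the last column for adverse events and vital signs is Week 6/drop, and early terminators have the week 6 assessments when they leave.

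**After the study.** "Subjects who complete the study will have the option of receiving two clinical care visits" (Section V, Subject Dosing and Visit schedule). The visits are roughly monthly, over up to three months, and are described as a courtesy to help the participant find ongoing care. The paragraph ends: "No research data will be collected at these follow-up visits".

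**After stopping for safety.** Section V, Study Discontinuation Criteria: "If study participation is discontinued due to safety reasons, participants will receive two followup visits". Their stated purpose is referral. Nothing is said about data.

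**Serious events.** "All solriamfetol treatment-emergent serious adverse events (initial and follow-up) that require collection per protocol will be reported" to the company within one business day of awareness. The definition of a serious event requires a temporal association with participation but gives no number of days. Its examples include "the development of drug dependency or drug abuse".

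**The concern.** Spontaneously reported adverse events are the main tolerability outcome (Section V, Assessments and Instruments). They are therefore research data, and the sentence barring research data at the later visits covers them on its face. A site following that sentence could see a participant whose event was open at week 6, learn whether it resolved, and have no instruction to record it. The same holds for a non-serious event that begins after the study drug is stopped.

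At stake is how complete the safety description is in a pilot with up to 30 participants per arm. At that size a handful of events without a known outcome, or of post-treatment events never recorded, could change the description of tolerability. Participants who stop for safety reasons are where open events are most likely, and they are the group the protocol undertakes to see twice more.

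**Working it through.** The protocol gives no figure to reproduce, and no rate from which to estimate how many events are affected. The check is a count of the schedule and a comparison of the sections.

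1. **Scheduled collection.** By the text, adverse events are recorded at weeks 1 to 6, which is 6 visits. The Visual Timeline also marks baseline, which the text excludes. That mismatch does not affect where collection ends.

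2. **Later contacts.** Two visits are offered at the end of the study, and two are provided after a safety discontinuation. Adverse-event collection is planned at 0 of 2 in each case: by explicit bar in the first, by silence in the second.

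3. **Time after last dose.** Because each dose assignment runs to the next visit, dosing in completers runs up to the week 6 visit. Planned observation after that visit is 0 days. Early terminators may differ: if dosing stopped before the drop visit, that visit can capture some off-drug events.

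4. **Other post-dose periods in the plan.** Exclusion criterion 3 (Section III) requires contraception for 1 month after the last dose. Adverse-event collection has no corresponding period.

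5. **Open events.** No section requires an event to be followed to resolution. The recorded attributes (description, severity, expectedness, relatedness) include neither an outcome nor a stop date.

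6. **Serious events.** Reporting covers "serious adverse events (initial and follow-up) that require collection per protocol will be reported". The protocol never says for how long collection is required, so after week 6 the clause refers to a rule that is not there. Follow-up reports are expected, but no procedure says when or how the follow-up information is obtained.

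7. **Reach of the bar.** The paragraph containing it opens with follow-up visits offered to subjects generally and then speaks of completers. The visits after a safety discontinuation are in a different section, are the same in number and serve a similar referral purpose. A site could reasonably apply the bar to them or not.

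8. **Routes that remain after week 6.**

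| Type of event | Route after the last study visit |
|---|---|
| Serious event | Report to the company on awareness |
| Unanticipated problem | Report to the Human Research Committee within 5 working days/7 calendar days of awareness |
| Pregnancy | Outcome sought with permission (Section V, Safety Assessments) |
| Non-serious event, new or continuing | None planned |

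The last row is the gap. It includes non-serious moderate or severe events, and moderate or severe is the grade that the test of Hypothesis 2 reviews.

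**The case against.** The strongest reply is that the care visits are a clinical courtesy and that safety reporting runs on a separate track. Serious-event reporting depends on awareness, not on a visit. Section V also allows contact by phone or in person as needed, and clinicians can be reached by pager at all hours. Follow-up on a serious event can be obtained that way without using the care visits for research. This stands. A reader might infer that the bar and the serious-event reporting rule contradict each other, or that follow-up reports cannot be made without breaching the bar. The documents do not support either reading: the two passages are in tension only.

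A reader might also infer that every event open at week 6, and every later event, is lost. That goes too far. The routes in the table above remain for serious events, unanticipated problems and pregnancies, and a drop visit may capture some off-drug events.

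Third, Section VI tests Hypothesis 2 by reviewing the occurrence of moderate or severe events and describing reasons for dropout. For a participant who stops because of an event, both can be recorded by the drop visit, and resolution is not an analysis variable. This stands too, and it rules out the inference that the planned tolerability comparison is invalid.

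Finally, events seen up to three months later may reflect new treatment. That is a reason to report them separately, not a reason to leave them unrecorded.

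What the reply does not meet is the case of non-serious events. Awareness-based routes and the pager depend on someone volunteering information, and nothing carries a non-serious event into the dataset after the last study visit.

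**Conclusion.** The point holds as a gap in safety follow-up that is cheap to close. Collection is scheduled at six weekly visits and at neither of the two later contacts. No window after the last dose is stated, and no rule covers open events. The number of events affected cannot be estimated from the documents.

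The conclusion rests on two readings. One is that research data includes adverse events, which follows from their role as the main tolerability outcome. The other is that completers dose up to the week 6 visit, which follows from the dosing schedule. Whether the bar reaches the visits after a safety discontinuation is unclear and is not assumed; the absence of any instruction to record data there is enough. The on-treatment count of events and the reasons for dropout remain usable as planned.

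**What to change.** - In Section V, Subject Dosing and Visit schedule, limit the bar at the later visits to efficacy data.
- State one adverse-event and serious-adverse-event collection window after the last dose, the same for both arms and for completers and early terminators. Its length is for the sponsor and investigator to set.
- Within that window, record at the existing contacts (the care visits and the visits after a safety discontinuation) any new adverse event, the outcome of each event open at the final or drop visit, and all serious adverse events.
- In Section VI, report post-treatment events separately from on-treatment events, because new treatment may have started.
- Reconcile the visit schedule, Adverse Event Assessment and Reporting (including the serious-event definition), Study Discontinuation Criteria and the Visual Timeline, so that each gives the same end of collection.

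**Cost.** A short form at contacts that already exist, and changes to protocol and consent wording. Capture will be incomplete because the completer visits are optional, and some recorded events will be confounded by new care. A phone call to those who decline a visit would improve capture but is optional and not needed for the fix.

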Randomization to active or placebo will occur once a subject is scheduled for a baseline visit, when the clinical trials pharmacy will be given a subject name that the pharmacy will associate with a number identifier. We have extensive experience maintaining blinding, wherein we have our central Mass General Hospital Clinical Trials Pharmacy pharmacy serve as the only part of the greater trial team that is aware of the assignment to active or placebo during study participation. The trials pharmacy will receive products identified by the sponsor as active or placebo fill, over-encapsulate these products to look identical, bottle these products with unique identifiers, maintains the placeboactive ratio, and maintain blinding until study completion. For the purpose of the final analysis, the official clinical database will not be unblinded until medical/scientific review has been completed, protocol violators have been identified (if appropriate), and data collection has been declared complete. In the extreme event where subject safety will be compromised by maintaining the blind, eg. an adverse event where treatment is dependent on knowing if they were on active or placebo medication, we will unblind the status of the subject's study agent, following emergency protocols in place in our department and institution.

Assessments and Instruments:

Our primary endpoint will be change in the Adult ADHD Investigator Symptom Rating Scale (AISRS), the instrument we will use to evaluate ADHD symptom burden. We also will evaluate spontaneously reported adverse events as our main outcome of tolerability. At screening evaluation, AISRS ratings and concurrent medication treatments will be recorded. In addition, at screening or baseline, a brief demographic interview will be conducted to obtain information used to calculate socioeconomic status.

Demographic information, including socioeconomic status data, will collected for each participant.²⁴

During the study, the following assessments and instruments will be used:

Clinician rated assessments (rated at each in-office study visit, unless otherwise noted):

- Global Assessment of Functioning (GAF) scale. The GAF will assess global functioning using a scale from 1 (worst) to 100 (best). This will be collected at all study visits, excluding the screening visit.
- Clinical Global Impressions (CGI) scale for ADHD. The CGI is a measure of illness severity, improvement, and efficacy of treatment.

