If clinically appropriate, any subjects taking medication exclusionary to the study must be tapered off this medication prior to baseline visit for the length of 5 half-lives of the medication, corresponding to 95% of the agent leaving the participant's system), plus several days to assess the participant off medication. Individuals may participate if they prefer not to take a previously optimized treatment for documentable reasons such as side effects, perceived risks, personal preference, or lack of sufficient benefit. However, subjects will not enter the study if it would require tapering or otherwise stopping a medication that is optimally and comfortably managing a clinical concern likely to cause unaccommodated suffering of the participant. For example, a participant may prefer to participate in the trial after stopping a stimulant treatment that causes side effects but helps them in school, during a summer vacation period where the consequences of stopping and participating will be accommodated by lack of school participation and more time to complete daily tasks. Medication tapers will be monitored by the study clinician in agreement with the research subject and in consultation with the prescribing physician. No subject will be removed from a stable and effective treatment regimen for the purposes of participating in the study.

Subjects will be instructed not to take any medications or supplements that are contraindicated by exclusion criteria for the study. All new medications and supplements started during the study will be reviewed by the PI, and subjects may be dropped from study participation, but their data will be retained in the safety and intent-to-treat analyses with PI discretion.

In addition, any subject found to be taking medication listed as exclusionary during the course of the study or the seven days prior to randomization will be evaluated by the PI for ongoing eligibility.

Study Discontinuation Criteria

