Data obtained from this study will not identify the subjects individually. Subjects will be assigned code-names and ID numbers. Data obtained from our studies may be published, but no subjects will be identified individually in these publications. Original research-related records may be reviewed by the Partners Human Research Committee, and regulatory authorities, for the purpose of verifying clinical trial procedures and/or data. Information may be held and processed on a computer. Access to these computerized records will be password protected and restricted to study staff. Subjects will only be contacted regarding future studies if they indicate that they are interested in being contacted by initialing in the specific section of the consent form.

Email communication:

Any email communication will be done using Send Secure encryption per Partners polcy, unless a subject has authorized non-secure email communication. Before sending or responding to an unencrypted email message to an individual, the individual must acknowledge understanding of, and agreement to, accept the risks as communicated to them via the following language "The Partners standard is to send email securely. This requires you to initially set up and activate an account with a password. You can then use the password to access secure emails sent to you from Partners HealthCare. If you prefer, we can send you "unencrypted" email that is not secure and could result in the unauthorized use or disclosure of your information. If you want to receive communications by unencrypted email despite these risks, Partners HealthCare will not be held responsible. Your preference to receive unencrypted email will apply to emails sent from this research group/study only." This language will be copied into an email response to an individual, or may be read over the phone to the individual, or an individual could agree by reading this in person and signing this statement, or simply by agreeing verbally.

VIII. POTENTIAL BENEFITS

There may be no direct benefit to subjects participating in this study. Potential benefits to the participants include education about ADHD, a trial of a supplement that could be continued after the

study, and the opportunity to contribute to medical science and thus help others with similar difficulties.

VIII. Visual Timeline of Key Study Elements

	Eval.	Baseline (Visit 0)	Week	Week 2	Week 3	Week 4	Week 5	Week 6/drop
Consent	х							
Eligibility	х							

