Vital Signs (BP, pulse)		X*	х	х	х	х	х	x
Clinician Evaluation	x							
AISRS	х	х	х	х	х	х	х	х
ADHD-RS	X*							х
CGI ratings		х	х	х	х	х	х	х
GAF		х	х	х	х	х	х	х
Adverse Events		x	х	х	х	x	x	х
Concomitant Medications		х	х	х	х	х	х	x
BRIEF-A		X*						х
ASR	X*							
ESS		X*						х
PSQI		X*						х
Pill counting				х		х		х
Pregnancy test	х							х

^{*} Can be completed at either evaluation or baseline visit as long as those visits are within 10 days

^{**}If a subject terminates participation early, all assessments at week 6 will be made at study completion.

IX. Monitoring and Quality Assurance

The Principal Investigator will meet regularly with study staff to address procedural issues and the study coordinator will audit each subject's data within 48 hours of each study visit. Furthermore, all data will be audited by the study statistician with the assistance of the database manager on a regular basis to ensure the progress of the study and confirm that all necessary data is being collected and can be transitioned to the statistical package smoothly. Co-investigators are actively involved in the monitoring and quality assurance of these trials. Periodic quality assurance audits will ensure accuracy and completeness of all subject documents, IRB files and correspondence, and the informed consent documentation.

XI. Telehealth Remote study procedures

Subjects will be offered the option to participate via remote telehealth. Individuals may choose a mixture of in-person and telehealth visits, or just one or the other, as suits scheduling convenience or prudent safety practice. For example, during a public health infectious disease crisis such as the COVID-19 pandemic, risks to participants may be reduced by remote televisits. We will not conduct in-person visits unless approved by Partners healthcare and Massachusetts General Hospital.

Recent Virtual Visit Clinical Growth for COVID-19

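### The text excludes the baseline visit from adverse event recording but the schedule marks it; with no new-or-worsened rule, complaints present before dosing may be counted as on-treatment events

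*Combined protocol and SAP*

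**What the plan says.** All references are to the combined protocol and SAP.

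- **Section V, Assessments and Instruments.** Adverse experiences are "collected at all visits excluding the screening and baseline visits". The same section makes them a key outcome: "We also will evaluate spontaneously reported adverse events as our main outcome of tolerability".
- **Section V, Adverse Event Assessment and Reporting.** It repeats that "adverse events will be recorded at all visits other than screening and baseline". It then lists what is noted for each event: "Investigators will characterize adverse event by description, note the severity (mild, moderate, or severe), whether it is expected (yes or no), relatedness". Onset, and whether the complaint was present before the first dose, are not listed.
- **Visual Timeline of Key Study Elements.** The row "Adverse Events" is blank at evaluation and marked at Baseline (Visit 0) and at every weekly visit to week 6 or drop-out. The baseline mark has no asterisk, so the footnote about evaluation and baseline assessments does not apply to it.
- **Section VI.** The main look at Hypothesis 2 reviews events graded moderate or worse and describes why participants left. A further summary reports, by arm, the same event recorded at least twice in one participant. Neither refers to baseline status.
- **Section VII.** The drug's common reactions are given as insomnia, anxiety, headache, nausea and reduced appetite.

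**The concern.** Every reaction on the Section VII list is also an ordinary complaint that a participant may have before dosing. Some participants will have recently stopped another medicine: Section V, Concomitant Medications / Treatments, requires a taper of five half-lives "plus several days to assess the participant off medication". To tell a drug effect from a continuing complaint, the plan needs either a record from before the first dose or a note of when the complaint began, together with a counting rule that uses it.

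The text and the schedule disagree on whether the baseline record is taken, and the plan states no counting rule. At stake is how the main tolerability outcome reads: the absolute event rate on solriamfetol, and its contrast with placebo in a pilot of up to 30 participants per arm. The repeated-event summary is especially exposed, because a persistent complaint mentioned at any two of the six weekly visits would qualify, whereas a short-lived drug effect might be recorded only once.

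**Working it through.** **1. Is the contradiction real, or an artefact of a broken table?** I aligned the schedule rows with the eight visit columns and used three other rows as controls.

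| Row | Marks | Columns marked |
|---|---|---|
| Adverse events | 7 | Baseline, weeks 1–6 |
| CGI | 7 | Baseline, weeks 1–6 |
| AISRS | 8 | Evaluation, baseline, weeks 1–6 |
| Pregnancy test | 2 | Evaluation, week 6 |

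The control rows fall where the text puts them, so the columns have not shifted. The baseline mark for adverse events is genuine and conflicts with two statements in Section V.

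**2. What pre-dose information exists if the text is followed?**

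| Complaint (Section VII) | Pre-dose source specified |
|---|---|
| Insomnia | PSQI; ESS for sleepiness |
| Anxiety | ASR; psychiatric assessment |
| Headache, nausea, appetite | None specified beyond general medical history |

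No passage says that any of these sources is used to classify an adverse event. Section III also lets scales completed within the year before screening stand without being repeated, so some scores may be old.

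**3. How large could the effect be?** The documents give no event rates, so there is no plan figure to reproduce and every rate below is an assumption. Let *p* be the true rate of new events and *b* the proportion with a complaint already present, equal in both arms, independent of new events, and all counted.

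Recorded rate = *b* + (1 − *b*) × *p*. Difference between arms = (1 − *b*) × (0.25 − 0.10) = (1 − *b*) × 0.15.

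| *b* | Active, *p* = 0.25 | Placebo, *p* = 0.10 | Difference |
|---|---|---|---|
| 0 | 25.0% | 10.0% | 15.0 points |
| 0.10 | 0.10 + 0.90 × 0.25 = 32.5% | 0.10 + 0.90 × 0.10 = 19.0% | 13.5 points |
| 0.20 | 0.20 + 0.80 × 0.25 = 40.0% | 0.20 + 0.80 × 0.10 = 28.0% | 12.0 points |
| 0.30 | 0.30 + 0.70 × 0.25 = 47.5% | 0.30 + 0.70 × 0.10 = 37.0% | 10.5 points |

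A second assumed pair, 30% versus 10%, behaves the same way: at *b* = 0.40 the recorded rates are 58% and 46%, so a 20-point difference becomes 12.

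**4. Set against chance.** With 30 per arm and no background, the standard error of the difference is √[(0.25 × 0.75 + 0.10 × 0.90)/30] = √0.00925, or about 9.6 points. The shrinkage of 1.5 to 4.5 points is smaller than that, and chance imbalance in background complaints could move the observed contrast either way. The rise in absolute rates, 7.5 to 22.5 points on active and 9 to 27 on placebo, is the larger effect.

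**The case against.** Three stronger readings are tempting, and the documents do not support them.

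- **That pre-existing complaints are counted.** No passage says so. The plan only fails to prevent it.
- **That there is no pre-dose symptom information.** Even if baseline is skipped for adverse events, the plan has medical history, a psychiatric assessment, vital signs, the ASR, the PSQI and the ESS. These partly cover sleep, sleepiness and anxiety. The remaining gap is headache, nausea and appetite, and the missing link from any of these data to event classification.
- **That the term treatment-emergent cannot be applied.** It occurs once, undefined, for serious events reported to the company, and not for the tolerability outcome. A serious event can usually be dated against the first dose without a baseline symptom list.

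There are also reasons to expect a smaller effect than the illustration shows. Events are reported spontaneously, so long-standing, unchanged complaints need not all be volunteered. The main review is limited to moderate or severe events, which removes mild background complaints. It is descriptive, with no powered between-arm test to weaken. Investigators can rate an event as unrelated, and the taper rule requires several days beyond five half-lives and concerns only those who taper.

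Most of this stands, and it makes the table an upper bound for its chosen inputs. It does not remove the point. The two sections still disagree. Section VI counts occurrence, not related events, so the relatedness rating does not filter the count. The repeated-event summary is not described as restricted by severity.

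**Conclusion.** The contradiction between Section V and the schedule is established and must be reconciled. The consequence is a risk. If the text is followed, complaints present before the first dose may enter the count, because no onset field is listed and Section VI has no new-or-worsened rule. Following the schedule alone would not remove the risk, since nothing says how a baseline entry is to be used.

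The expected direction is higher recorded rates in both arms and a narrower contrast. The loss of 1.5 to 4.5 points from a 15-point difference rests on assumed rates, equal background in both arms, independence, and every background complaint being counted. In a placebo-controlled pilot of 60 this is a worthwhile, inexpensive improvement to the main tolerability outcome. It does not threaten the trial's primary efficacy comparison.

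**What to change.** 1. Amend both statements in Section V to agree with the schedule, so that baseline is included.
2. At the baseline visit, before the first dose, record current complaints with the same open question and the same mild/moderate/severe grading used at weeks 1–6. Using the same question matters: a symptom checklist at baseline followed by spontaneous reports later would make ascertainment unequal before and after dosing.
3. Add one field to the adverse event form: onset before or after the first dose. This also catches a complaint that was present but not mentioned at baseline.
4. In Section VI, count an adverse event only if it is new, or worse in severity, relative to the baseline record. Apply this to the moderate-or-severe review and to the repeated-event summary.

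The cost is a few minutes at a visit that already takes place, one form field, and a few sentences in Sections V and VI. Reported absolute event rates will be somewhat lower than under an unrestricted count, and the report should state the counting rule so that readers can see why.
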